#### 1.0 INTRODUCTION

## 1.1 Open Fractures

Open fractures represent some of the most severe musculoskeletal injuries. Due to their highenergy mechanisms, these extremity fractures are accompanied by soft-tissue injuries that contribute to unacceptably poor outcomes. The Fluid Lavage of Open Wounds (FLOW) trial of 2,447 open fracture patients reported a 13.2% incidence of open fracture-related reoperations;  however, these study events were even more common in open wounds with severe contamination (29.8%, 95% confidence interval (CI): 22.6–38.1%) and in patients with higher grades of injury (Gustilo-Anderson Type III: 18.0%, 95% CI: 15.6–20.7%). Ultimately, complications from open fractures lead to prolonged morbidity, loss of function, and potential limb loss.

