## 4.6.5 Evaluation of Site Performance and Removal of Clinical Sites

After every two recruitment periods (approximately every four months), each site will be evaluated for continued participation in the trial. Sites with <90% of eligible patients receiving the allocated solution, differential adherence between study solutions, <95% follow-up of the primary outcome, <90% follow-up of the secondary outcome, incomplete data submission, or other threats to data quality or the validity of the study may be withdrawn from the trial. In the event a site is withdrawn, data collection will be completed for all enrolled participants and these data will be included in the final study analysis.

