major study outcomes by telephone, text, or email contact with the participant or the provided alternate contacts. Given these are standard of care visits and the participants will be receiving ongoing orthopaedic care for their acute fractures, minimal loss to follow-up is expected. Using these techniques, we expect greater than 95% follow-up at 3 months and 90% follow-up at 12 months post-fracture.

Participants will not be deemed lost to follow-up until the 12-month visit is overdue and all attempts to contact the participant have been exhausted. Participants will not be withdrawn from the study if the study protocol was not adhered to (e.g., allocated treatment not received, missed follow-up visits, etc.). The reasons for participants being withdrawn from the study will be documented (e.g., withdrawal of consent or lost to follow up).

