**Table 5: Sample Size Assumptions** 

Baseline SSI Risk	10% Povidone- Iodine Risk Ratio	10% Povidone- Iodine Odds Ratio	Sample Size	Sample Size Increased by 10%
10.0%	0.62	0.59	1600	1760
10.0%	0.65	0.63	1960	2100
10.0%	0.67	0.65	2200	2420
10.0%	0.70	0.68	2600	2860
12.5%	0.62	0.59	1300	1440
12.5%	0.65	0.62	1400	1540
12.5%	0.67	0.64	1600	1760
12.5%	0.70	0.67	1800	1980
14.0%	0.62	0.58	1200	1320
14.0%	0.65	0.61	1300	1440
14.0%	0.67	0.64	1500	1660
14.0%	0.70	0.67	1800	1980

**Note:** \*Between cluster ICC = 0.028; Between cluster variance\* = 0.095; Between period variance = 0; Number of clusters = 10; Number of periods = 2; Alpha = 0.05

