## 5.2.4 Sensitivity Analyses

Assessment of the sensitivity or robustness of the findings to the key assumptions is essential in trials. The following sensitivity analyses may be conducted to explore the effects of alternative analysis models, alternative missing data approaches, balancing prognostic imbalance, as-treated analyses, variability in co-interventions, and alternative definitions of SSI.

- 1) *Using different analysis models:* There are several methods for analyzing cluster randomized crossover trials. Therefore, our sensitivity analyses will explore alternative multi-level models with different correlation structures for the error.
- 2) Different methods of handling missing data: There are several methods of handling missing data in trials. Multiple imputation assumes that the data are missing at random—an assumption that is not verifiable in practice. Other imputation methods will be used such as worst case scenario to impute missing data and assess the robustness of the results. For the worst case scenario analysis, we will assume that a random proportion of participants lost to follow-up experienced a study event. For this sensitivity analysis, the proportion assumed to experience a study event will be equivalent to the upper confidence interval of the observed pooled event rate for each study outcome.
- 3) Adjusted analyses for prognostic imbalance: We will also perform sensitivity analyses that assume prognostic imbalance between the two treatment groups based on the following key variables known to be risk factors for SSI or reoperation after open fracture: Gustilo fracture type, lower extremity fracture, wound contamination, time from injury to first debridement, antiseptic wound dressing in the emergency department, method of fixation, wound closure at initial debridement, age, work-related injury, and employment status.  Adjusted analyses including the above risk factors and treatment group as independent variables will be performed for the SSI and reoperation outcomes.

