2	Different missing data approach	SSI / Reoperation	Binary	10% povidone- iodine will be more effective than CHG	Multi-level regression models with missing data imputed using worst-case scenario	
3	Baseline prognostic imbalance	SSI / Reoperation	Binary	10% povidone- iodine will be more effective than CHG	Multi-level regression models with prognostic variables & treatment group	
4	As-treated analysis	SSI / Reoperation	Binary	10% povidone- iodine will be more effective than CHG	Multi-level regression models using "as treated" treatment group	
5	Co-intervention variability	SSI / Reoperation	Binary	Cluster- and period- variability is related to co-interventions	Censoring of cluster(s) and/or period(s) with differences in co- interventions	
6	Exploratory SSI definitions	FRI / CDC SSI within 1 year	Binary	10% povidone- iodine will be more effective than CHG	Multi-level regression models	

**Note:** CHG = 4% chlorhexidine gluconate; SSI = Surgical Site Infection; FRI = Fracture Related Infection; CDC = Centers for Disease Control and Prevention.

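### The worst-case missing-data analysis gives lost patients in both arms the same event rate, so it never tests a higher rate among missing povidone-iodine patients than among missing CHG patients

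*Combined protocol and SAP*

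**What the plan says.** Sections 5.2.1 and 5.2.2 make multiple imputation under missing at random the primary approach for both outcomes. Section 5.2.4, item 2, accepts that this assumption cannot be verified and offers a worst-case imputation as the robustness check. The rule has two parts. On who receives events: "we will assume that a random proportion of participants lost to follow-up experienced a study event". On how many: "the proportion assumed to experience a study event will be equivalent to the upper confidence interval of the observed pooled event rate", set separately for each outcome. Treatment group is not mentioned, and a pooled rate combines both arms. The item does not say what confidence level applies or whether the interval allows for clustering.

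Table 8, row 2, repeats the method as "Multi-level regression models with missing data imputed using worst-case scenario" and lists no alternative. The document describes no arm-specific, delta-adjusted or tipping-point analysis.

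On the expected amount of missing data, section 4.8.4 states: "we expect greater than 95% follow-up at 3 months and 90% follow-up at 12 months post-fracture". Section 4.6.5 allows a site to be withdrawn for "<95% follow-up of the primary outcome, <90% follow-up of the secondary outcome".

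**The concern.** The hypothesis is that povidone-iodine reduces events. The missing-data pattern that would damage that claim is an excess of unseen events among lost iodine patients relative to lost CHG patients. A common rate sets that difference to zero. It tests whether the effect survives dilution, not whether it survives loss that differs adversely between arms.

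The stake is one of interpretation. A report that follows the stated rule could say that the result withstood a worst case when no adverse difference between arms had been tried. This matters most for 12-month reoperation, where about one patient in ten is expected to be missing.

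**Working it through.** **Inputs.** CHG SSI rate 12.5% and risk ratio (RR) 0.65; reoperation baseline 13% with a similar effect expected (section 5.1). N = 1,540 (Table 5), taken as 770 per arm. Loss of 5% for SSI and 10% for reoperation (section 4.8.4), assumed equal by arm. Cluster variance 0.095 and 10 clusters (section 5.1, Table 5). Assumptions of this check: expected counts, a 95% Wald limit, a pooled two-proportion z-test, imputed outcomes treated as observed, and no clustering or between-imputation variance in the tests.

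**The plan's own figures.** 1,400 × 1.10 = 1,540. On the logit scale, 0.095 / (0.095 + π²/3) = 0.095 / 3.385 = 0.028, which matches "Between cluster ICC = 0.028". The stated ICC is therefore a logit-scale quantity.

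**Step 1: the imputed rate u, ignoring clustering.** u = p̄ + 1.96 √(p̄(1−p̄)/n), where p̄ is the pooled observed rate and n the number observed.
- SSI: p̄ = (0.125 + 0.08125)/2 = 0.1031, n = 1,463, u = 0.1031 + 0.0156 = 0.119.
- Reoperation: p̄ = (0.130 + 0.0845)/2 = 0.1073, n = 1,386, u = 0.1073 + 0.0163 = 0.124.

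**Step 2: the same limit allowing for clustering.** A design effect for a proportion needs the ICC on the proportion scale, approximately 0.095 × p̄(1−p̄), or about 0.009 for both outcomes. With 10 clusters, DE = 1 + (n/10 − 1) × 0.009 = 2.31 (SSI) and 2.24 (reoperation). Then u = 0.1031 + 0.0156√2.31 = 0.127 and 0.1073 + 0.0163√2.24 = 0.132. With 12 clusters the limits are about 12.6% and 13.0%.

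**Step 3: what the rule does.** With equal loss l, each arm's rate becomes (1−l)p + l·u. The arms then differ by (1−l)(p_CHG − p_iodine), which keeps its sign whatever u is.

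| Outcome, observed RR 0.65 | CHG after rule | Iodine after rule | RR | p |
|---|---|---|---|---|
| SSI, 5% loss | 0.1247 | 0.0831 | 0.667 | 0.008 |
| Reoperation, 10% loss | 0.1294 | 0.0884 | 0.683 | 0.010 |

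With the clustered limit, the RRs are 0.668 and 0.685.

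**Step 4: letting the arms differ.** Hold missing CHG patients at their observed rate and raise the rate q in missing iodine patients until z falls below 1.96. The iodine rate is (1−l)p_iodine + l·q.

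| Outcome | Observed RR | Tipping q | Events among missing iodine patients | Events at the observed iodine rate |
|---|---|---|---|---|
| SSI, 5% loss | 0.65 | about 33% | 12.8 of 38.5 | 3.1 |
| Reoperation, 10% loss | 0.65 | about 22% | 17.1 of 77 | 6.5 |
| Reoperation, 10% loss | 0.70 (assumed) | about 16% | 12.6 of 77 | 7.0 |

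In the last row the stated rule gives u = 0.127, RR 0.729 and p = 0.029 (0.030 with the clustered limit). Raising both arms' missing rate to 18.0%, the type III reoperation rate in section 1.1, still gives only p = 0.032. Significance is lost through a difference between the arms, which the rule never introduces.

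**Step 5: outer bounds.** If every missing iodine patient and no missing CHG patient had an event, at observed RR 0.65, the RR would be (59.4 + 38.5)/91.4 = 1.07 for SSI and (58.6 + 77)/90.1 = 1.50 for reoperation. These are limits, not plausible scenarios.

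**The case against.** The rule is openly defined, so anyone who reads it knows what was done. It is also not neutral: at planning values it places missing iodine patients about 4 points above their observed rate and leaves missing CHG patients within a point of theirs, which works against the hypothesised benefit. Item 2 gives worst case only as an example, the list of sensitivity analyses is optional, and a separate detailed SAP is promised. Follow-up is pursued through record review, outside-hospital records and alternate contacts, which limits missingness. At the effect size the protocol expects, the tipping rates are demanding: 22% for reoperation is 1.7 times the CHG rate and 2.6 times the observed iodine rate, and 33% for SSI is about four times the observed iodine rate. The 16% figure depends on an assumed weaker effect.

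All of this stands and it limits the weight of the point. It does not supply the missing test. Room for other methods is not a specification, and an arm-specific analysis chosen after results are known carries less conviction.

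Three stronger readings are not supported:
- A reader might infer that loss is likely to be selective by arm because site staff are unblinded (section 4.5). No section says or suggests that it is.
- A reader might infer that the SSI conclusion is fragile. With more than 95% follow-up expected, it is not, at the planned effect.
- A reader might put 0.028 directly into a design effect and obtain an imputed rate near 14%. That ICC is on the logit scale, and the corresponding limit is about 13%.

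**Conclusion.** The point holds as a modest one. The analysis labelled worst case sets the difference between arms among missing patients to zero. It departs from missing at random and shrinks the effect a little: RR 0.65 becomes about 0.67 for SSI and 0.68-0.69 for reoperation. With equal loss it cannot change the direction. With unequal loss it can cross 1 only when the observed RR is already close to 1; for example, 15% iodine and 5% CHG loss turns a reoperation RR of 0.99 into 1.005.

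The practical consequence is confined mainly to 12-month reoperation with an effect somewhat weaker than planned. There the stated rule would report p of about 0.03, while roughly 16% events in missing iodine patients against 13% in missing CHG patients would remove significance. The thresholds come from a simplified calculation, and those from the planned multilevel model with proper imputation variance will differ. The primary estimate, type I error and power are not touched.

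**What to change.** In section 5.2.4, item 2, and Table 8, row 2:
- Rename the present rule common-rate imputation, and state its confidence level and whether the interval allows for clustering.
- Add a pre-specified tipping-point analysis (delta-adjusted multiple imputation), at least for 12-month reoperation. It should vary the event rate among missing participants independently by arm, use the loss actually seen in each arm and fit the primary multilevel model.
- Report the pairs of arm-specific rates at which the conclusion changes, with a judgement on whether they are plausible.
- Show the all-versus-none extremes as bounds only.

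The cost is wording in the SAP plus modest programming and reporting, with no extra patients or data. The resulting robustness statement may be less favourable than the one the present rule would give.

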## 4.5 Blinding

The orthopaedic team (including the study coordinators) cannot be blinded to the treatment allocation as the antiseptic solutions are visually distinguishable and these individuals need to lead the implementation of the cluster-crossover protocol at their clinical site. The Adjudication Committee Members and data analysts will be blinded to the study treatment. All interpretation of study results will initially be done in a blinded manner by developing two interpretations of the results. One interpretation will assume treatment A is povidone-iodine, the other interpretation will assume it is CHG. Once the data interpretations for each assumption are finalized, the data will be unblinded and the correct interpretation will be accepted.

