## 4.6.6 Application of Pre-Operative Antiseptic Skin Solutions

Each solution will be applied to the injured area in accordance with the Food and Drug Administration (FDA) and Health Canada approved manufacturer's directions for use. While the

application and minimum drying time for both study solutions are very similar, local study personnel will provide standardized in-service (training) for orthopaedic surgeons, operating room technicians, and nurses at each participating hospital prior to the run-in phases for each of the two randomized interventions. This training should include reviewing the manufacturers' directions for use to help minimize incorrect application at clinical sites that may not routinely use both solutions. In addition, the manufacturers may also provide demonstration videos and posters for continued refresher training for each solution.

The study protocol will mandate the antiseptic skin solution to be used in each intervention phase (Sections 4.4, 4.6.1, 4.6.2, 4.6.3, and 4.6.4); however, the protocol will remain pragmatic to variability in other co-intervention steps performed during the entire pre-operative skin preparation process performed in the operating room. Based on individual surgeon preference, this often includes mechanically removing visible dirt or debris with a scrub brush, and/or cleaning the limb with isopropyl alcohol or antiseptic scrub solution. These additional skin preparation steps will be permitted provided that: 1) the final skin preparation step prior to surgical incision is the application of the allocated antiseptic solution; and, 2) participating surgeons continue to use the same skin preparation co-interventions in both intervention phases. Co-interventions that contain the opposite active ingredient from the current intervention phase (e.g., using a chlorhexidine scrub brush during the povidone-iodine intervention phase, or conversely, using a povidone-iodine scrub during the chlorhexidine intervention phase) should be avoided; however, deviations from this recommendation will be permitted in order to maintain pragmatic *flexibility of delivery* and reflect real-world clinical practice. The details of all operating room antiseptic co-interventions will be documented.

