## 4.6.7 Povidone-Iodine Treatment

The povidone-iodine solution will contain 10% povidone-iodine (1% free iodine) in purified water as the only active ingredient. Products that list other inactive ingredients, including alcohol, will be permitted. The brand of the solution will be left to the discretion of the clinical site, although Methods Center personnel will confirm that the chosen solution is acceptable. Acceptable brands include, but are not limited to, Betadine® [Purdue Products, L.P. Stamford, CT] and Scrub Care® [Cardinal Health, Dublin, OH]. Clinical site personnel will store and handle the povidone-iodine solution as per the manufacturers' recommendations. Operating room personnel will apply the solution to the operative site as the final preoperative skin antisepsis preparation immediately prior to commencing surgical fixation. They will apply the solution as per manufacturer's directions for use (e.g., technique of application, duration of application, drying time, drying techniques, replacement of draping, etc.).

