## 4.8.4 Data Collection and Participant Follow-up

After obtaining informed consent, study personnel will record the baseline data on the study CRFs. They will obtain this information directly from the participant or proxy, from the participant's medical chart, and the participant's treating orthopaedic surgeon and other health care providers. Data collection points include patient characteristics and injury details such as age, gender, comorbidities, mechanism of injury, socioeconomic status, and other injuries. Study personnel will also record the characteristics of up to three open fracture regions including the location, fracture severity, size of the wound, and degree of soft tissue injury using the Gustilo classification. 8,17,24

Surgical data and in-hospital data will be collected throughout the participant's hospital stay. Detailed information will be collected regarding the surgical management of the open fracture(s), including the time to irrigation and debridement. For each open fracture region, study personnel will record the use of staged debridements, the presence or lack of skin closure between debridements, and the use of local antibiotics at the wound. The method(s) of initial and final fracture management will also be captured. Lastly, study personnel will record the use of negative pressure wound therapy for open wounds or in the presence of open wounds surgically closed. These treatment decisions are hypothesized to be associated markers of injury severity and potential confounders of the study interventions.

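### The adjusted analysis for baseline prognostic imbalance includes wound closure and method of fixation, which can be decided after the antiseptic is applied; if the solution influences them, the adjusted estimate is distorted.

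*Combined protocol and SAP*

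**What the plan says.** Section 5.2.4, item 3, lists ten risk factors for infection or reoperation, among them "method of fixation, wound closure at initial debridement", and commits to a model containing all of them beside treatment: "Adjusted analyses including the above risk factors and treatment group as independent variables will be performed for the SSI and reoperation outcomes". Table 8, row 3, labels this analysis "Baseline prognostic imbalance". The lead-in to the section is softer: "The following sensitivity analyses may be conducted".

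Three other places fix the order of events:

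- Section 4.6.6 permits other skin preparation steps provided that "the final skin preparation step prior to surgical incision is the application of the allocated antiseptic solution". Sections 4.6.7 and 4.6.8 describe each solution as the "final preoperative skin antisepsis preparation immediately prior to commencing surgical fixation".
- Section 4.5 says that the orthopaedic team "cannot be blinded to the treatment allocation as the antiseptic solutions are visually distinguishable".
- Section 4.8.4 records both initial and final fracture management, along with staged debridement, skin closure and wound therapy, and comments: "These treatment decisions are hypothesized to be associated markers of injury severity and potential confounders of the study interventions".

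The primary and secondary models in section 5.2.2 contain treatment group only, so item 3 is the one covariate-adjusted treatment effect that the plan specifies.

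**The concern.** Being a known risk factor is not enough to make a variable suitable for an imbalance check. It must also be something that the treatment could not have changed. Closure at the first debridement does not meet that condition, and neither does definitive fixation after staged surgery.

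Two distortions are possible if the solution affects these choices. If the choice in turn affects infection, adjusting for it removes that part of the solution's effect. If the choice also reflects injury severity that the other covariates do not capture, conditioning on it links treatment to severity even though allocation was randomised.

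The check matters in this trial because patients may be enrolled up to three weeks after fracture, often after surgery, by staff who know the allocation (sections 4.3.1, 4.5 and 7.2). A reader will look to item 3 for assurance that the arms were comparable. With post-treatment variables in the model, a gap from the primary result could be mistaken for confounding, and agreement could be mistaken for reassurance.

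**Working it through.** **Timing of each covariate**

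| Covariate in item 3 | Position relative to first application |
|---|---|
| Age, employment status, work-related injury | Before |
| Lower extremity, Gustilo type, contamination | Set by the injury; graded by unblinded staff |
| Time to first debridement, emergency-department dressing | Before, though the period's allocation is already known |
| Wound closure at initial debridement | After: it follows the incision, which follows application |
| Method of fixation | Mixed: an initial plan may come before; definitive fixation after staged surgery comes after |

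Fixation has a further difficulty. Under section 4.8.1 an SSI counts from the date of fracture, so an infection can precede definitive fixation. If item 3 means final fixation, the model may adjust for a consequence of the outcome.

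**Is there a figure to reproduce?** The plan gives none for this point. The planning effect serves as a base. CHG risk is 12.5% and the risk ratio 0.65 (section 5.1), so the povidone-iodine risk is 0.125 × 0.65 = 0.08125. The odds ratio is (0.08125/0.91875) / (0.125/0.875) = 0.0884/0.1429 = 0.62, which matches Table 5.

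**Loss of part of the effect.** The following are assumptions, because the documents give no values: 50% of wounds closed under CHG, closure halves the odds of SSI, and the solution's odds ratio at fixed closure is 0.62.

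- CHG: risk 0.1619 if open and 0.0881 if closed; 0.5 × 0.1619 + 0.5 × 0.0881 = 0.125.
- Povidone-iodine: multiplying each odds by 0.62 gives 0.1070 if open and 0.0565 if closed.
- With closure at 60% (10 points higher): 0.4 × 0.1070 + 0.6 × 0.0565 = 0.0767. Total odds ratio = (0.0767/0.9233) / 0.1429 = 0.581.

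| Closure difference | Povidone-iodine risk | Total OR | Closure-adjusted OR | Adjusted / total |
|---|---|---|---|---|
| 0 points | 8.17% | 0.623 | 0.620 | 0.995 |
| 3 | 8.02% | 0.611 | 0.620 | 1.016 |
| 5 | 7.92% | 0.602 | 0.620 | 1.030 |
| 10 | 7.67% | 0.581 | 0.620 | 1.066 |
| 20 | 7.16% | 0.540 | 0.620 | 1.148 |

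The small shift at zero difference is non-collapsibility of the odds ratio, not bias. Taking CHG closure as 35% or 65% moves the 10-point ratio to 1.06 or 1.07, and the 20-point ratio to 1.14 or 1.16.

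A second exact enumeration used an unfavourable choice, such as a wound left open, with 35% prevalence under CHG, and a direct OR of 0.65. The choice multiplied the odds of SSI by 2 to 3. The share of the log odds ratio removed by adjustment was 3 to 4% when the solution-to-choice OR was 0.9, 9 to 13% at 0.75, and 19 to 27% at 0.5.

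**Path through severity.** Here the solution truly has no effect on SSI and neither does the choice, but unmeasured severity affects both choice and SSI (assumed ORs of 3 to 5). The adjusted OR moves from 1.00 to 1.006–1.011, 1.016–1.030 and 1.037–1.070 for the same three solution-to-choice ORs.

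**The case against.** The strongest reply is that no path is documented. Nothing in the protocol says that the solution changes how often wounds are closed or how fractures are fixed. Section 1.7 reports views on tissue toxicity only as a reason for choosing a solution. Without such a path the bias disappears. That stands, and it is why the size is unknown.

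Scale is a fair point too. With 1,400 analysed (700 per arm), the standard error of the log odds ratio, ignoring clustering, is √(1/87.5 + 1/612.5 + 1/56.9 + 1/643.1) = 0.18. The 95% interval therefore spans a factor of exp(1.96 × 0.18) ≈ 1.4 each way, and a 6% shift is small beside that. However, the primary and adjusted estimates come from the same patients, so a gap between them will be interpreted directly.

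Closure and fixation can also be defended as proxies for severity, as section 4.8.4 suggests. Gustilo type and contamination already serve that purpose without depending on what the surgeon does after application.

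Some stronger inferences are not supported:

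- That the main result is compromised. The primary model has no such covariates, item 3 is one sensitivity analysis, and the lead-in leaves it optional although the item itself says it will be done.
- That method of fixation is always post-treatment. An initial plan may precede skin preparation; closure and definitive fixation are the clear cases.
- That emergency-department dressing and time to debridement must also go. Both precede the first application.
- That section 4.8.4 builds in the same error. It describes data collection and specifies no model.

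**Conclusion.** The point holds as a defect in one sensitivity analysis. By the protocol's own sequence, wound closure at initial debridement and any definitive fixation after staged surgery follow treatment, so they do not belong in a model labelled as a baseline check. The fixation variable is also undefined, because initial or final is not stated.

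The size depends wholly on whether, and how strongly, the solution affects these choices. It is roughly 1 to 3% on the odds ratio for a 3 to 5 point closure difference and roughly 6 to 15% for 10 to 20 points, given an assumed closure odds ratio of 0.5 and closure near 50%. It is essentially nil if there is no such influence. The case for acting is that the error is clear and cheap to remove, not that a large bias has been shown.

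**What to change.** In section 5.2.4 item 3, Table 8 row 3 and the separate SAP still to be written, state that the adjusted model is limited to characteristics of the patient, the injury and pre-operative care that the first application cannot change. Eight of the ten listed covariates qualify: Gustilo type, contamination, lower extremity, time from injury to first debridement, emergency-department dressing, age, work-related injury and employment status.

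Remove wound closure and method of fixation from that model. Report them by arm as descriptive process measures, or in a separately labelled model that is not offered as a baseline-imbalance check. If fixation is used anywhere, say whether initial or final is meant.

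Rewording the remark on confounders in section 4.8.4 is optional and changes no analysis.

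The cost is wording only, with no new data and no change to the sample size. The downside is that two prognostic variables leave one sensitivity model. The change also does not remove the fact that Gustilo type and contamination are graded by unblinded staff.
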